7.3.2 Statistical methods

The on-treatment pregnancy rate will be estimated using the primary pregnancy analysis cycles based on the Pearl Index (pregnancies per 100 woman-years of follow-up)

$$Pearl\ Index = \frac{Number\ of\ Pregnancies}{Total\ Number\ of\ Pregnancy\ Analysis\ Cycles} \times 1300$$

and its exact 95% confidence interval (CI) derived using a Poisson distribution assumption as

Lower 95% CI (Pearl Index)
$$= \frac{\chi_{0.025, df=v1}^{2}}{2 \times Total \ Number \ of \ Pregnancy \ Analysis \ Cycles} \times 1300$$

and

Upper 95% CI (Pearl Index)
$$= \frac{\chi_{0.975, df=v2}^{2}}{2 \times Total \ Number \ of \ Pregnancy \ Analysis \ Cycles} \times 1300$$

where $v1=2 \times \text{Number of Pregnancies and } v2=2 \times (\text{Number of Pregnancies} +1)$. Analysis will be done for each year of use and cumulatively through year three.

In addition, the typical use Pearl Index estimated by including all Study Cycles in the denominator of Pearl Index estimator will be reported. Similarly, by using all Study Cycles, the Kaplan-Meier product limit method with cycle as the "time" unit will also be used to summarize the typical use cumulative probability of pregnancy through the study follow-up period. Ninety five percent confidence intervals about the estimates of the cumulative probability of pregnancy will be provided, using the method of Peto et al. to calculate the standard error for the probabilities. Moreover, two additional sensitivity analyses will be considered to handle those cycles using other contraceptive methods in the Kaplan-Meier product limit method. The first approach is to exclude those cycles from the analysis and the remaining cycles will be renumbered to provide contiguous cycles (e.g., if Cycle 3 is excluded, Cycle 4 will be treated as Cycle 3, and so forth). The second approach is to allow participants to leave and re-enter the risk set of pregnancy of the Kaplan-Meier product limit method if they had a cycle using other contraceptive methods between two primary pregnancy analysis cycles.

In a separate analysis, these same approaches will be applied to analyze pregnancy using secondary pregnancy analysis cycles.

7.4. Analysis of Secondary Endpoint - IUD Discontinuations

The User Population will be used for IUD discontinuation analysis. Descriptive statistics will be calculated by pooling data across sites. In addition, a supporting analysis will be performed using the Per Protocol Population if more than 5% of participants in the User Population are excluded.

7.4.1 Definition of variables

Discontinuation Event: The endpoint of discontinuation is time to IUD removal for any reason or exit from the trial at the end of the study.

Reasons for discontinuation¹ are recorded in the IUD Removal and End of Trial sections of the data capture system. The following table shows the origin of the data and the endpoint classification that will be used in the analysis:

¹ A discontinuation event might have more than one reason.

Completed study participation Not sexually active anymore Wants to get pregnant Increased menstrual blood loss Intermenstrual bleeding/spotting Intermenstrual pain side effects Menstrual pain IUD was completely expelled had to be removed by the clinician IUD perforation Method failure (pregnancy with IUD in situ) Other Completed Study Completed Study Not sexually active anymore Increased menstrual blood loss Intermenstrual blood loss Intermenstrual blood loss Intermenstrual pain side effects Menstrual pain Spontaneous complete expulsion Malpositioned IUD removed by clinician (not considered partial expulsion) IUD perforation Pregnancy with IUD in situ Other *** Other ***
Not sexually active anymore Not sexually active anymore Wants to get pregnant Desire for pregnancy Increased menstrual blood loss Adverse event** Intermenstrual bleeding/spotting Intermenstrual bleeding/spotting Intermenstrual pain side effects Adverse event** Menstrual pain Adverse event** IUD was completely expelled Spontaneous complete expulsion IUD was malpositioned and had to be removed by the clinician Malpositioned IUD but not expelled IUD perforation Method failure (pregnancy with IUD in situ) Method failure (pregnancy with IUD in situ) Pregnancy Other Other*** Adverse event Other adverse event
Wants to get pregnantDesire for pregnancyIncreased menstrual blood lossAdverse event**Increased menstrual blood lossIntermenstrual bleeding/spottingAdverse event**Intermenstrual bleeding/spottingIntermenstrual pain side effectsAdverse event**Intermenstrual pain side effectsMenstrual painAdverse event**Menstrual painIUD was completely expelled bull on the complete of linicianSpontaneous complete expulsionSpontaneous complete expulsionIUD was malpositioned and had to be removed by the clinicianMalpositioned IUD but not expelledMalpositioned IUD removed by clinician (not considered partial expulsion)IUD perforationIUD perforationMethod failure (pregnancy with IUD in situ)Pregnancy Pregnancy with IUD in situOtherOther***Other adverse eventOther adverse event
Increased menstrual blood loss Intermenstrual bleeding/spotting Intermenstrual bleeding/spotting Intermenstrual pain side effects Menstrual pain IUD was completely expelled had to be removed by the clinician IUD perforation Method failure (pregnancy with IUD in situ) Increased menstrual blood loss Intermenstrual blood loss Intermenstrual bleeding/spotting Intermenstrual pain bleeding/spotting Intermenstrual pain side effects Menstrual pain Menstrual pain Spontaneous complete expulsion Malpositioned IUD but not expelled by clinician (not considered partial expulsion) IUD perforation Pregnancy Pregnancy Other Other Other Other Other Other adverse event
loss Intermenstrual Adverse event** Intermenstrual bleeding/spotting Intermenstrual pain side effects Adverse event** Intermenstrual pain side effects Menstrual pain Adverse event** Menstrual pain IUD was completely expelled had to be removed by the clinician Spontaneous complete expulsion Spontaneous complete expulsion IUD perforation Malpositioned IUD but not expelled Malpositioned IUD removed by clinician (not considered partial expulsion) IUD perforation IUD perforation Method failure (pregnancy with IUD in situ) Pregnancy with IUD in situ Other Other*** Adverse event Other adverse event
Intermenstrual bleeding/spotting Intermenstrual pain side effects Menstrual pain IUD was completely expelled had to be removed by the clinician IUD perforation Method failure (pregnancy with IUD in situ) Intermenstrual bleeding/spotting Intermenstrual pain bleeding/spotting Intermenstrual pain side effects Menstrual pain Spontaneous complete expulsion Spontaneous complete expulsion Malpositioned IUD but not expelled by clinician (not considered partial expulsion) IUD perforation Pregnancy Pregnancy Pregnancy Other Other Other Other Other other other adverse event
bleeding/spottingbleeding/spottingIntermenstrual pain side effectsAdverse event**Intermenstrual pain side effectsMenstrual painAdverse event**Menstrual painIUD was completely expelled ExpulsionSpontaneous complete expulsionSpontaneous complete expulsionIUD was malpositioned and had to be removed by the clinicianMalpositioned IUD but not expelledMalpositioned IUD removed by clinician (not considered partial expulsion)IUD perforationIUD perforationMethod failure (pregnancy with IUD in situ)Pregnancy OtherPregnancy with IUD in situOtherOther***Adverse eventOther adverse event
Intermenstrual pain side effects Menstrual pain IUD was completely expelled IUD was malpositioned and had to be removed by the clinician IUD perforation Method failure (pregnancy with IUD in situ) Other Other Adverse event** Menstrual pain Spontaneous complete expulsion Spontaneous complete expulsion Malpositioned IUD but not expulsion Malpositioned IUD removed by clinician (not considered partial expulsion) IUD perforation Pregnancy Pregnancy Pregnancy with IUD in situ Other Other Other Other***
effectseffectsMenstrual painAdverse event**Menstrual painIUD was completely expelledSpontaneous complete expulsionSpontaneous complete expulsionIUD was malpositioned and had to be removed by the clinicianMalpositioned IUD but not expelledMalpositioned IUD removed by clinician (not considered partial expulsion)IUD perforationIUD perforationMethod failure (pregnancy with IUD in situ)Pregnancy with IUD in situOtherOther***Adverse eventOther adverse event
Menstrual painAdverse event**Menstrual painIUD was completely expelledSpontaneous complete expulsionSpontaneous complete expulsionIUD was malpositioned and had to be removed by the clinicianMalpositioned IUD but not expelledMalpositioned IUD removed by clinician (not considered partial expulsion)IUD perforationIUD perforationMethod failure (pregnancy with IUD in situ)Pregnancy with IUD in situOtherOther***Adverse eventOther adverse event
IUD was completely expelledSpontaneous complete expulsionSpontaneous complete expulsionIUD was malpositioned and had to be removed by the clinicianMalpositioned IUD but not expelledMalpositioned IUD removed by clinician (not considered partial expulsion)IUD perforationIUD perforationMethod failure (pregnancy with IUD in situ)Pregnancy with IUD in situOtherOther***Adverse eventOther adverse event
IUD was malpositioned and had to be removed by the clinician IUD perforation Method failure (pregnancy with IUD in situ) Other Other Expulsion Malpositioned IUD removed by clinician (not considered partial expulsion) IUD perforation Pregnancy Pregnancy Pregnancy with IUD in situ Other Other Other Other Other adverse event
IUD was malpositioned and had to be removed by the clinicianMalpositioned IUD but not expelledMalpositioned IUD removed by clinician (not considered partial expulsion)IUD perforationIUD perforationMethod failure (pregnancy with IUD in situ)Pregnancy OtherPregnancy with IUD in situOtherOther***Adverse eventOther adverse event
had to be removed by the clinician (not considered partial expulsion) IUD perforation Method failure (pregnancy with IUD in situ) Other Other Other Other Other Other adverse event
clinician partial expulsion) IUD perforation IUD perforation Method failure (pregnancy with IUD in situ with IUD in situ) Other Other Other Adverse event Other adverse event
IUD perforation IUD perforation Method failure (pregnancy with IUD in situ) Pregnancy with IUD in situ Other Other*** Adverse event Other adverse event
Method failure (pregnancy with IUD in situ)Pregnancy with IUD in situOtherOtherOther***Adverse eventOther adverse event
with IUD in situ) Other Other Other Other Other adverse event
Other Other Other** Adverse event Other adverse event
Adverse event Other adverse event
(without nre coded event
(without pre-coded event
from IUD removal CRF)
Withdrew Consent Withdrew Consent
Protocol Violation Protocol Violation
Investigator/Sponsor Investigator/Sponsor
Decision Decision
Use of Prohibited Medication Use of Prohibited Medication
Uterus not sounded or <5.5 Uterus not sounded or <5.5
Failed IUD placement Failed IUD placement
attempt attempt
Spontaneous partial expulsion Spontaneous partial expulsion
(IUD in cervix or at os) (IUD in cervix or at os)
Accidental self- Accidental self-
removal/dislodgement removal/dislodgement
Lost to Follow-up Lost to Follow-up

^{*} For presentation in tables, additional groupings may be created

^{**} If corresponding, pre-coded IUD removal reason was also reported

*** Other reasons will be further subdivided if enough cases exist to combine them with a new label

7.4.2 Statistical methods

The frequency and the percentage of women who complete the study or who leave the study for specific reasons, including loss to follow-up, will be tabulated. The percentage of discontinuation for each of the categories outlined above will be provided by study groups for the entire population. The duration of IUD exposure will be presented in summary tables using means, standard deviations, medians, interquartile ranges, minima and maxima by treatment group, site and overall.

For early discontinuation probabilities and comparative analyses, participants who complete full participation will be classified as censored. The product limit method (Kaplan and Meier, 1958) will be used to estimate 12-month, 24-month and 36-month cumulative probabilities (and associated 95% confidence intervals) for IUD discontinuation. A stratified logrank test by study site will be used to compare the discontinuation probabilities between the two groups of women, separately over the 12 and 36 months study periods. A non-stratified logrank test will be used if too few events (i.e., < 5) occur in one or more study sites.

As a supporting analysis, Cox's proportional hazards regression (Cox, 1972) will be used to assess differences in the risk of discontinuation between study groups, controlling for covariates. Suspected prognostic factors such as sociodemographic characteristics (i.e., age, education, relationship status), reproductive history (i.e., parity) and previous contraceptive experience (e.g., hormonal method use) will also be considered if they are significantly related to the outcome at the alpha=0.10 level in analyses of groups combined.

The assumption of proportional hazards will be assessed graphically and by testing for the significance of interaction terms between time (or functions of time) and other variables in the model if there is no time-dependent covariate in the model. If the proportional hazard assumption is violated, further data transformations or other methods will be considered. All interactions will be tested at the alpha=0.05 level.

To measure time to discontinuation due to a specific reason, such as menstrual pain, the same analysis strategy will be used. Competing reasons for removal will be considered independent and censored such as IUD expulsion, failed IUD insertion, uterine perforation, pregnancy, personal/non-medical reasons, and other medically-related reasons.

Specific reasons for discontinuation will also be grouped into broader categories in further exploratory analyses. "Discontinuation due to side effects" will include bleeding and pain reasons. Personal (non-medical) reasons will include not sexually active, wants to get pregnant, and withdrew consent for study fatigue (burden) issues. The same analysis strategy will be used for these exploratory analyses.

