# 19 STATISTICAL METHODS AND CONSIDERATIONS

# 19.1 Sample Size

Below is the original estimate for the 95% upper bound of the Pearl Index for the Mona Lisa Cu IUD arm if we had randomized 800 subjects to that treatment. Since this protocol has been amended to randomize approximately 880 Mona Lisa Cu IUD subjects, the estimated 95% upper bound of the Pearl Index would be slightly lower due to the larger sample size. In addition, the power to detect differences in 12-month IUD continuations rates will be slightly higher than the original power presented below.

Randomizing 800 women to the Mona Lisa Cu IUD will provide approximately 17,700 cycles for the primary efficacy analysis among women under 36 years old at time of enrollment,

assuming 13 cycles of use per year with 84.3% evaluable cycles, an exponential discontinuation rate of 0.2 (i.e., approximately 20% per year), and 37 months of prescribed follow-up per woman. Based on this enrollment total and follow-up rate, the upper bound of the Pearl Index (pregnancies per 100 women-years of follow-up) would be approximately 1.0 if 6 pregnancies were observed (see table).

Table 09: Expected Pearl Index (pregnancies per 100 women-years of follow-up) among women under 36 years old at time of enrollment and 95% CI for Pearl Index as a function of observed number of pregnancies, assuming 800 women are randomized to Mona Lisa Cu IUD and 51.2% method continuation at month 37

Observed pregnancies	Pearl Index	95% CI
0	0.0	0.0-0.3
1	0.1	0.0-0.4
2	0.1	0.0-0.5
3	0.2	0.0-0.6
4	0.3	0.1-0.8
5	0.4	0.1-0.9
6	0.4	0.2-1.0

In terms of estimating and comparing standard 12-month IUD continuation rates, the study will achieve approximately 87% power to detect a 10% greater 12-month continuation rate for the Mona Lisa Cu IUD using a two-sided  $\alpha$ =0.05 level log-rank test, assuming the 12-month probability of continuation for ParaGard is 70% and allowing for up to 5% of women lost to follow-up.

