The proportions of subjects experiencing any other side effects will be calculated with corresponding exact confidence intervals for each group, and compared the difference between groups by Fisher's exact tests or the Cochran-Mantel-Haenszel tests. Generalized linear model approaches for repeated occurrence side effect outcomes might be used to further assess the differences in the incidence of adverse events between study groups.

Overall satisfaction with the method will be summarized and compared between groups at the final study visit using two-sided Mantel-Haenszel chi-square tests. Similarly, the same statistical analysis methods will be used to describe ease of product insertion between groups. Changes in pain with and shortly after insertion from baseline will be described by the summary statistics (mean, median, inter-quartile, etc.) of visual analog scale measurements. The Mann-Whitney test or the analysis of variance method will be used to compare the changes in pain between groups.

For all secondary objectives, comparisons between groups will be made using two-sided 0.05 level significance tests, without adjustment for multiple comparisons.

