1. INTRODUCTION

This is a multi-site, participant-blinded, randomized clinical trial. The study will randomize 1000 eligible participants in a 4:1 ratio to two different copper IUDs: 800 to Mona Lisa NT Cu380 Mini and 200 to ParaGard. Recruitment will be approximately 80% nulliparous and 20% parous women, and approximately 10% of women will be \geq 36 years old.

The total duration of the study is expected to be five years. The total duration for each participant is expected to be approximately 37 months. Each woman will attend a baseline visit, followed by visits at 6 weeks, 3 months, 6 months, 12 months, 24 months and 37 months, with telephones calls at 9, 18 and 30 months. Each subject will participate for up to 37 months (or less if the product is removed or expelled). Participants will use a home pregnancy test 17 days after Exit Visit procedures or any time she suspects that she may be pregnant, and report the results to their respective sites via telephone.

The analysis plan provides additional details regarding the planned statistical analysis of the study protocol (version 2.0, 09May17). Tables, figures and listings shells will be developed and included as an appendix to a future version of the plan.

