5.7. Lost to Follow-up Population

Lost to Follow-up Population is a subset of User Population who have the following experiences:

- left the clinic with the IUD in situ and
- had no documented IUD removal and
- whose last known use of the IUD was earlier than 37 months after IUD placement.

A subset of the Lost to Follow-up Population that has no follow-up data whatsoever is referred to as "Completely" Lost to Follow-up. Participants' baseline characteristics will be analyzed if more than 5% of the User Population are excluded from the Lost to Follow-up Population.

The following table summarizes various analyses conducted on each analysis population.

Table 1: Analyses performed on each analysis population

	Analysis						
Population				Safety and other			
1 opulation			IUD	secondary			
	Baseline	Efficacy	Discontinuation	endpoint			
Screened							
ITT	✓			✓			
Treated	√*			√ ‡			
User	✓		✓	✓			
Per protocol	✓		√ ***	√ ***			
Efficacy Analysis	✓	✓					
Lost to Follow-up	✓ **						

^{*} Analysis will be performed if > 5% of ITT Population is excluded.

^{**} Analysis will be performed if > 5% of User Population is lost to follow-up.

^{****}Analysis will be performed if > 5% of User Population is excluded.

[‡] Analysis will be performed for safety and other secondary endpoints observed during the insertion process.

The following table summarizes various study participant status included in each analysis population.

Table 2: Study participant status included in each analysis population

	Population						
Study participant status	Screened	ITT	Treated	User	Per Protocol	Efficacy	LTF
Early situations							I
Screen failures	✓						
Eligible but not enrolled	✓						
Enrolled	✓						
Protocol violation on enrollment	✓						
Post-randomization situations		•					•
Medical contraindication*		✓					
No successful sounding of the		✓					
uterus							
Uterine depth < 5.5cm		✓					
No IUD placement attempt**		✓					
Randomization errors (as		✓					
assigned)							
Randomization errors (as			✓	✓		✓	✓
treated)							
IUD placement attempts							
Attempted but failed IUD placement		✓	✓				
Successful IUD placement but		√	√	√			
immediate removal per							
request by participant							
Successful IUD placement		√	✓	√	√	√	√
and leaves clinic with IUD in							
situ							

^{*} e.g., discovering mucopurulent cervical discharge before/during/after sounding the uterus ** IUD placement attempt is defined as handling the product and attempting to place it

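### The SAP has no censoring rule for women lost to follow-up in the IUD discontinuation analysis; read literally, 7.4.2 with the reason table counts them as events, against 7.4.1, 5.7 and the protocol's power basis

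*SAP*

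**What the plan says.** **Censoring.** SAP 7.4.2 sets out the Kaplan-Meier estimates, the log-rank test and the supporting Cox model for discontinuation. For the all-cause analysis it says "participants who complete full participation will be classified as censored" and names nobody else. A later paragraph censors competing reasons for removal, but only in the reason-specific analyses, and its examples do not include loss to follow-up.

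**Reasons.** The table in SAP 7.4.1 maps form entries to the endpoint classification to be used in the analysis. Its last row reads "Lost to Follow-up Lost to Follow-up", which I take to be the form entry and its classification. SAP 7.4.2 then tabulates reasons for leaving the study, loss among them.

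**Event.** SAP 7.4.1 defines the endpoint as time to IUD removal, whatever the reason, or to exit at the end of the study.

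**Who is lost.** SAP 5.7 joins three conditions: the woman went home with the device in place, she "had no documented IUD removal and" her last known use was before month 37.

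**Elsewhere.** SAP section 6 describes lost women as discontinuing early and censors them explicitly, but only for the primary pregnancy analysis. Protocol 19.1 states the power for 12-month continuation while "allowing for up to 5% of women lost to follow-up".

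**The concern.** Two sets of passages lead to different datasets. SAP 7.4.2 read with the reason table makes a lost woman an event. The event definition in 7.4.1 read with 5.7 leaves her without one. The bare definition cannot be the whole event rule either, because expulsion is not removal and enters the endpoint only through the table. A programmer therefore cannot set the table aside, and the table includes loss.

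The authors wrote a rule for lost women in the pregnancy analysis and none here. Continuation is the first-listed secondary objective and the only between-arm comparison with a stated power. Counting women last known to have the IUD in place as discontinued would lower continuation in both arms, shrink the contrast, and let a difference in tracing between arms appear as a difference between devices.

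**Working it through.** **Inputs**
- Protocol 19.1: "the study will achieve approximately 87% power to detect a 10% greater 12-month continuation rate for the Mona Lisa Cu IUD"; the 12-month "probability of continuation for ParaGard is 70% and allowing for up to 5% of women lost to follow-up". I read the effect as 80% versus 70%.
- Protocol 19.2.2: "comparisons between groups will be made using two-sided 0.05 level significance tests".
- Allocation behind the stated power (SAP section 1): "800 to Mona Lisa NT Cu380 Mini and 200 to ParaGard". The current protocol has about 880 and 220.
- Assumed: 5% loss in each arm by 12 months, independent of discontinuation. The protocol gives only an upper limit of 5%, not split by arm.

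**Step 1: the plan's own figure.** The protocol does not name its formula. Freedman's, for 4:1 allocation, is

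power = Φ( √(4 × events) × (1 − HR) / (1 + 4 × HR) − 1.96 ).

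- HR = ln 0.80 / ln 0.70 = 0.626.
- With 5% taken out as non-events, events = 0.95 × (800 × 0.20 + 200 × 0.30) = 209.
- √836 = 28.91, and 28.91 × 0.374 / 3.502 = 3.09. Power = Φ(1.13) = 87.1%, matching the stated 87%.

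The match is consistent with loss being treated as a non-event but does not prove it. On the same inputs other methods give 77.4% (Schoenfeld), 82.7% (pooled two proportions) and 85.5% (variance of the log hazard ratio). The last gives 87.2% with no loss at all.

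**Step 2: what the estimates would read.** If lost women are events:
- Mini: 0.80 × 0.95 = 0.760.
- ParaGard: 0.70 × 0.95 = 0.665.
- The difference falls from 10 to 9.5 points, and HR becomes ln 0.76 / ln 0.665 = 0.673.

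**Step 3: power, Freedman.**
- 880/220, censored: events = 0.95 × (176 + 66) = 229.9; Φ(3.24 − 1.96) = 90.0%.
- 880/220, as events: events = 880 × 0.24 + 220 × 0.335 = 284.9; Φ(2.99 − 1.96) = 84.9%.
- 800/200, as events: events = 192 + 67 = 259; Φ(2.85 − 1.96) = 81.4%, against 87.1% censored.

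**Step 4: power, simulation.** Unstratified log-rank test, exponential times, 12 months, 20,000 runs, 5% loss in each arm.

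| Allocation | Lost censored | Lost as events |
|---|---|---|
| 880/220 | 88% | 82% |
| 800/200 | 85% | 79% |

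A separate 6,000-run check at 800/200 gave 85.0% and 77.5%. Across methods and runs the drop is about 5 to 7 points.

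**Step 5: unequal loss (illustrative rates only).** Same simulation at 880/220.

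| True continuation, Mini / ParaGard | Loss, Mini / ParaGard | Rejects if censored | Rejects if events |
|---|---|---|---|
| 80% / 70% | 5% / 2% | 88% | 62% |
| 80% / 70% | 2% / 5% | 88% | 95% |
| 75% / 75% | 5% / 10% | 5% | 21% |
| 75% / 75% | 3% / 6% | 5% | 11% |

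In the first row the apparent difference is 0.760 − 0.686 = 7.4 points; in the second, 0.784 − 0.665 = 11.9 points. In the last two rows there is no true difference, so the test's size is lost.

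**The case against.** The best reply is that the SAP already implies censoring. The sentence about completers has its own purpose: the endpoint definition includes exit at the end of the study, so without that sentence every completer would be an event. Lost women need no such exception, because they have no recorded removal and a Kaplan-Meier analysis censors anyone without an event. The table looks like a disposition list: it also holds study completion, which is censored, and failed placement, which cannot occur in the User Population analysed here. Neither the reasons in Protocol 19.2.2 nor the competing reasons in SAP 7.4.2 include loss.

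Much of this stands. A reader might infer that the SAP has decided to count lost women as discontinued. The documents do not support that: no passage says so, and 7.4.2 does not say that completers are the only women censored. What the reply does not remove is the conflict. The table is introduced as the classification for analysis, expulsion depends on it, and section 6 places lost women among those who discontinue early.

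Two limits on size also stand. A reader might carry the 5% forward to 36 months. The protocol states it only beside the 12-month comparison, and its exposure calculation uses a single 20% yearly discontinuation rate with no separate loss term, so loss may already be inside that rate. I give no 36-month figure. Nor do the documents show that lost women keep the IUD at the same rate as those followed.

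**Conclusion.** The point holds as an unresolved conflict that should be fixed, not as a settled wrong rule. The literal reading of 7.4.2 with the reason table makes loss an event; 7.4.1, 5.7 and Protocol 19.1 point the other way.

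With equal, independent loss of 5% by 12 months, the event reading lowers reported continuation by 4 points for the Mini and 3.5 for ParaGard and costs about 5 to 7 points of power. At 880/220 that leaves power at 82% to 85%, somewhat below the planned 87%. This is moderate, and smaller if loss is below 5%. Equal loss does not inflate the false-positive rate; unequal loss can bias the comparison in either direction, but the documents give no rates by arm, so that part shows what the open rule permits and is not a forecast. The simulations are unstratified, whereas the SAP plans to stratify by site.

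**What to change.** Add to SAP 7.4.2: women who leave without a documented discontinuation event (removal, expulsion, perforation or pregnancy), including those lost to follow-up or withdrawing consent with the IUD last known in place, are censored at the last contact at which the IUD was confirmed or reported in place. Specify lost-equals-discontinued as a sensitivity analysis, and report loss to follow-up by arm beside it. Naming all four events matters: a rule limited to removal and expulsion would drop perforation and pregnancy without a recorded removal, both of which Protocol 19.2.2 lists as discontinuation reasons.

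The cost is a short SAP amendment. No new data are needed, since Appendix 1 of the protocol has IUD status collected at every follow-up visit and, by the woman's report, at Calls 1 to 3. The rule should be fixed before the comparison is run, so that the choice cannot depend on the result.

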5.4. User Population

The User Population is a subset of Treated Population who had a successful IUD insertion. It includes participants who leave the clinic with the IUD in situ as well as those who have the product removed before leaving the clinic and exit from the study. This analysis population will mainly be used for analyzing discontinuation and safety and other secondary endpoints after a successful IUD insertion.

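### Discontinuation probabilities by reason, estimated as 1−KM with other removal reasons censored, overstate the share of users who leave for each reason; report cumulative incidence instead

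*SAP*

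**What the plan says.** SAP 7.4.2 states that the product-limit method "will be used to estimate 12-month, 24-month and 36-month cumulative probabilities" of IUD discontinuation, followed by log-rank tests and supporting Cox models. For single reasons it continues: "To measure time to discontinuation due to a specific reason, such as menstrual pain, the same analysis strategy will be used". The rule for the other reasons is "Competing reasons for removal will be considered independent and censored". For the broader groupings (side effects, personal reasons) it adds: "The same analysis strategy will be used for these exploratory analyses".

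The same section plans a simple tabulation: "The percentage of discontinuation for each of the categories outlined above will be provided by study groups". These percentages are not tied to 12, 24 or 36 months.

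Protocol 19.2.2 confirms that probabilities by reason are intended, not only hazard comparisons: directly after specifying Kaplan-Meier estimates and a log-rank test, it asks for similar summaries of the probabilities of discontinuation by reason. It mentions competing risk analysis only as a way to explore informative censoring that differs between groups. SAP 7.4.2 does not take this up, and the SAP plans no cumulative incidence function.

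On counting, the footnote in SAP 7.4.1 notes: "A discontinuation event might have more than one reason".

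**The concern.** A woman whose IUD has been expelled or removed for bleeding cannot later have it removed for pain. Those are competing events, not incomplete follow-up. Censoring them makes the product-limit estimate behave as if she could still leave for pain at the rate of the women who remain.

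A reader will take a 24-month probability of discontinuation for menstrual pain as the share of users who leave for pain by 24 months, and the 1−KM figure is larger than that share. At 36 months the report would also show a 1−KM figure and a crude percentage for the same reason, with no statement of why they differ. The reason figures would not add up to the all-cause figure. At stake is the description of why women stop using each device.

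**Working it through.** **Inputs.**
- All-cause discontinuation of about 20% per year (Protocol 19.1). The plan's own continuation figure reproduces as 0.8³ = 51.2%. Protocol Table 09 labels it month 37, but the arithmetic is 36 months. Continuation S is therefore 0.80, 0.64 and 0.512 at 12, 24 and 36 months.
- Reason shares of the hazard are not in the documents. I assume a constant share s, from 0.1 (a narrow reason) to 0.5 (a dominant one).
- Yearly ParaGard rates per 100 for years 1/2/3 (Protocol Appendix 7, label Table 2): pregnancy 0.7/0.3/0.6, expulsion 5.7/2.5/1.6, bleeding or pain 11.9/9.8/7.0, other medical 2.5/2.1/1.6. I treat these as single-decrement yearly rates, which is an assumption.

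**Step 1: excess for one reason.** With share s, 1−KM = 1 − S^s and cumulative incidence (CIF) = s(1 − S).

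| Month | s = 0.1: 1−KM vs CIF | Excess | s = 0.5: 1−KM vs CIF | Excess |
|---|---|---|---|---|
| 12 | 2.2% vs 2.0% | 0.2 | 10.6% vs 10.0% | 0.6 |
| 24 | 4.4% vs 3.6% | 0.8 | 20.0% vs 18.0% | 2.0 |
| 36 | 6.5% vs 4.9% | 1.6 | 28.4% vs 24.4% | 4.0 |

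For the narrow reason the relative excess is 0.76/3.6 = 21% at 24 months and 1.60/4.88 = 33% at 36. If the planned rate is read as a hazard of 0.2, so that S = exp(−0.2t), the 36-month excess is 1.3 to 3.4 points.

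**Step 2: additivity on the label rates.** Use yearly hazards −ln(1 − rate), constant within each year, and one reason per removal.

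| Month | Sum of 1−KM | All-cause |
|---|---|---|
| 12 | 20.8% | 19.6% |
| 24 | 34.1% | 31.0% |
| 36 | 43.3% | 38.2% |

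At 36 months, 1−KM vs CIF is 1.6 vs 1.2 (pregnancy), 9.5 vs 8.2 (expulsion), 26.1 vs 23.8 (bleeding or pain) and 6.1 vs 4.9 (other medical). The cumulative incidences add up to the all-cause figure, within rounding.

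**Step 3: do the crude percentages fill the gap?** With L = −ln 0.8 and a loss-to-follow-up hazard m, the crude percentage at 36 months is s·L/(L+m)·(1 − exp(−3(L+m))). Take m for 5% lost over three years, or for 5% lost per year. The result is 4.8% or 4.6% for s = 0.1 (CIF 4.9%) and 23.9% or 22.8% for s = 0.5 (CIF 24.4%). They come close at the end of study, but nothing corresponds to them at 12 or 24 months.

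**Step 4: is 1−KM the net probability?** Only under independence. Suppose two reasons at 0.10 per year share a gamma frailty with mean 1 and variance 1. At 36 months all-cause continuation is 1/(1 + 0.6) = 0.625. Then 1−KM = 1 − √0.625 = 20.9%, the true net probability is 1 − 1/1.3 = 23.1%, and the share leaving for the reason is 0.375/2 = 18.8%. The 1−KM figure matches neither.

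**Step 5: what cumulative incidence costs.** Give both arms the same reason hazard, 0.5L. Let ParaGard's total loss be 30% in year 1 (the 70% continuation in Protocol 19.1) and 20% per year after. At 36 months 1−KM is 28.4% in both arms. CIF is 0.5 × 48.8% = 24.4% for the test device. For ParaGard it is (0.1116/0.3567) × 0.30 + 0.7 × 0.5 × 0.36 = 22.0%. The 2.4-point difference comes entirely from the other reasons.

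**The case against.** The strongest reply is that the SAP openly states its censoring and independence assumptions, so a statistician can see that a net probability is meant; that table shells are still to come (SAP 1); and that the actual shares are tabulated anyway. Each part is true as far as it goes. But no wording tells a reader of the results that the figure is net, and the tabulated shares cover only the end of study.

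A second reply is that the two estimators answer different questions and the secondary objective is comparative. Step 5 shows that 1−KM can be the cleaner device contrast. That stands, and it is why log-rank and Cox should be kept.

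A third is size. Without loss to follow-up, the Greenwood 95% half-width is 1.96·S^s·√(s(1/S − 1)/n). For s = 0.1 this gives 1.0, 1.5 and 1.9 points at 12, 24 and 36 months with 880 women, and 2.0, 3.0 and 3.8 with 220. The excess lies inside the interval each time. In the cases computed it exceeds the half-width only for s = 0.5 at 36 months in the test arm (4.0 vs 3.3). This shows the effect is modest, but a systematic upward shift is not excused by sampling error.

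A fourth is that additivity depends on counting as well as on the estimator. This is correct: if every mentioned reason counts, cumulative incidences can also sum past the total.

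A reader might infer that the device comparisons are biased. The documents do not support that: log-rank and Cox with other reasons censored compare cause-specific hazards. A reader might also see an error in listing failed insertion among the censored reasons. The SAP says "The User Population will be used for IUD discontinuation analysis" and "The User Population is a subset of Treated Population who had a successful IUD insertion", so the item adds no events and is only clerical.

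**Conclusion.** The point holds for the reported probabilities by reason and goes no further. The 1−KM figures overstate the share leaving for each reason, whether or not the reasons are independent, and with one reason per removal they sum past all-cause discontinuation. The excess is about 0.2–0.6 point at 12 months, 0.8–2.0 at 24 and 1.6–4.0 at 36. These sizes rest on the planned 20% per year and on assumed constant hazard shares of 10% to 50%; the label illustration rests on reading its rates as single-decrement.

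It would go too far to call the planned figure a net probability without condition, since that needs independence. Nor do the documents support extending the problem to all-cause continuation, to the cause-specific tests or to the primary pregnancy endpoint. This is an inexpensive improvement to a secondary description, with little effect at 12 months.

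**What to change.** - In SAP 7.4.2, report 12-, 24- and 36-month probabilities by reason with the Aalen-Johansen cumulative incidence function. Treat other removal reasons as competing events and censor only loss to follow-up and study completion. Do the same for the grouped reasons.
- Keep log-rank and Cox as the between-device comparison, labelled cause-specific. Read cumulative-incidence differences beside them, because these also reflect the other reasons.
- If any 1−KM figure is kept, leave the independence assumption stated and label it 'net of other reasons, assuming independence'.
- State how a removal with several reasons is counted. If any mention counts, note that the figures may sum past the total. I see no such rule in 7.4.2, but the reason table in 7.4.1 is damaged in the text available to me, so check it first.
- Dropping failed insertion from the censoring list is optional tidying.

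The cost is SAP wording and a note in the SAP of the departure from Protocol 19.2.2, which Protocol 19.2 requires. The estimator needs no new data. A rule based on one primary reason would need that reason to be identifiable in the records, which the documents do not show. Loss to follow-up is still censored as independent.
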